8.5 Determination of Sample Size

The purpose of this study is to gather information on safety and effectiveness as a lead-in to a subsequent multi-center pivotal trial, and no therefore formal hypothesis testing is defined *a priori*. For this purpose, implant of up to 30 subjects is deemed sufficient for reasonable precision of estimation of study parameters. Based on prior pilot study (G170294) it is anticipated that there will be consented patients that do not get implanted. These non-implanted patients will be accounted for and documented.

8.6 Interim Analysis

No formal interim analysis for early stopping is specified. Accordingly, any analyses of study results which may be performed during study conduct will not be interpreted to permit early stopping of the study for success, although early stopping for safety is permitted as always.

8.7 Handling of Missing Data

Every effort will be made to reduce the incidence of missing data. The study will be conducted with proper screening of study subjects, complete training of participating investigators, study coordinators and monitors. All subject data that are available on subjects who drop out during the study will be included. Missing data will not otherwise be replaced or otherwise imputed, as the primary analysis is to be conducted on the ICH E9 definition of the full analysis set.

The number and proportion of subjects eligible for and compliant with each follow-up examination will be presented. Subjects who withdraw from the study will be tabulated with reasons for withdrawal.

8.8 Poolability of Outcomes

As no formal statistical hypotheses are to be tested, no formal assessment of poolability will be performed.

9. DATA MANAGEMENT

The sponsor will collect study data using paper or electronic case report forms (CRFs). Paper case report forms are filled out by designated site personnel, reviewed and approved by the investigator, submitted to the sponsor, and entered by the sponsor into a clinical data management system (CDMS). The investigator may be prompted by queries from the sponsor data management personnel or monitors to clarify, correct, or confirm data which are missing, out of range, or illogical.

10. PROTOCOL AMENDMENTS

The sponsor, as per MDR 2017/745 and national regulation, must submit and, where necessary, obtain approval from the EC and CA for all subsequent study amendments, such as protocol changes, IB changes, or changes to the Informed Consent Form.

11. PROTOCOL DEVIATIONS

Deviations to the clinical study protocol are not permitted except as necessary to protect the rights, safety and well-being of human subjects. These deviations shall be reported to the sponsor and as part of the final study report submitted to the EC.

When possible, investigators shall notify the sponsor prior to any deviation from the protocol. All non-emergent deviations will be noted on the appropriate case report form (CRF) and will be reviewed by monitors during monitoring visits.

The sponsor shall review all deviations to determine investigator protocol compliance. Action will be taken to secure compliance if repeated protocol non-compliance is noted. This may take the form of training, other corrective actions or, if necessary, disqualification of the investigator from the study.

12. DEVICE ACCOUNTABILITY

Investigational devices will only be shipped to qualified investigators. Each study device will be labeled for investigational use only and will contain an identifying lot and/or serial number. The date of receipt, use, disposition, subject identifier, and date of return (as applicable) will be recorded on a device accountability log for each device shipped to the site.

13. REGULATORY COMPLIANCE

This study will be conducted in compliance with current standard ISO 14155:2020 (Clinical Investigation of Medical Devices for Human Subjects – Good Clinical Practice), the ethical principles of the Declaration of Helsinki and European Medical Device Regulation MDR 2017/745, and other applicable regulatory requirements. The study protocol and consent must be approved by the responsible EC and per national regulations. Study activities must not commence prior to receipt of documentation of EC approval and Competent Authority approval by the site and sponsor. The Investigator and study staff must comply with the requirements of the EC.

14. INFORMED CONSENT PROCESS

An informed consent document suitable for use in this study, including the elements of informed consent in conformance with ISO 14155:2020. Iterations of this document must also include the elements of informed consent in conformance with ISO 14155:2020 must be approved by the reviewing Ethics Committee. Subjects must be presented with the most current EC approved version of the consent form for signature and study enrollment.

Country specific consent regulations and language requirements should be followed and incorporated into the consent document.

Prior to enrolling in this trial, the subject will review the informed consent materials with the investigator or appointed designee. The consent form and consent discussion should be in a language the subject understands.

In order to provide consent for study participation, each subject must be fully informed about the investigational device, requirements, risks and benefits, and must sign and date the informed consent form acknowledging that participation is voluntary. The subject will sign and date the approved study-specific

informed consent form prior to any study related procedure or testing being performed. However, historical and standard of care medical tests and records may be used to determine eligibility (e.g. imaging, lab tests).

Subjects may withdraw participation at any time during the investigation without sacrificing their rights as a patient or compromising their quality of medical care.

15. ADVERSE EVENTS, ADVERSE DEVICE EFFECTS AND DEVICE DEFICIENCIES

15.1 Definitions as per ISO 14155:2020 & MDR 2017/745

Adverse Event (AE): Any untoward medical occurrence, unintended disease or injury or any untoward clinical signs, including an abnormal laboratory findings, in subjects, users or other persons, in the context of a clinical investigation, whether or not related to the investigational medical device.

Note 1: This definition includes events related to the investigational medical device or the comparator.

Note 2: This definition includes events related to the procedures involved.

Note 3: For users or other persons, this definition is restricted to events related to the use of investigational medical devices or comparators.

Adverse Device Effect (ADE): Adverse event related to the use of an investigational medical device.

Note 1: This definition includes adverse events resulting from insufficient or inadequate instructions for use, deployment, implantation, installation, or operation, or any malfunction of the investigational medical device.

Note 2: This definition includes any event resulting from use error or from intentional misuse of the investigational medical device.

Note 3: This includes 'comparator' if the comparator is a medical device.

Serious Adverse Event (SAE): Any adverse event that led to any of the following:

a) Death,

b) serious deterioration in the health of the subject, that resulted in any of the following:

1) a life-threatening illness or injury,

2) a permanent impairment of a body structure or a body function,

3) hospitalization or prolongation of patient hospitalisation

4) medical or surgical intervention to prevent life-threatening illness or injury, or permanent impairment to a body structure or a body function,

5) chronic disease,

c) foetal distress, foetal death or a congenital physical or mental impairment or birth defect

Note 1: Planned hospitalization for a pre-existing condition, or a procedure required by the CIP, without serious deterioration in health, is not considered a serious adverse event.

Events that do not meet these criteria are considered non-serious.

Serious Adverse Device Effect (SADE): Adverse device effect that has resulted in any of the consequences characteristic of a serious adverse event.

Unanticipated Serious Adverse Device Effect (USADE): Serious adverse effect which by its nature, incidence, severity or outcome has not been identified in the current risk assessment.

Note 1: Anticipated serious adverse device effect (ASADE) is an effect which by its nature, incidence, severity or outcome has been identified in the risk assessment.

Device Deficiency: Any inadequacy in the identity, quality, durability, reliability, safety or performance of an investigational device, including malfunction, use errors or inadequacy in information supplied by the manufacturer;.

Note 1: Device deficiencies include malfunctions, use errors, and inadequacy in the information supplied by the manufacturer including labelling.

Note 2: This definition includes device deficiencies related to the investigational medical device or the comparator.

Use Error: User action or lack of user action while using the medical device that leads to a different result than that intended by the manufacturer or expected by the user.

Note 1: Use error includes the inability of the user to complete a task.

Note 2: Use errors can result from a mismatch between the characteristics of the user, user interface, task or use environment.

Note 3: Users might be aware or unaware that a use error has occurred.

Note 4: An unexpected physiological response of the patient is not by itself considered a use error.

Note 5: A malfunction of a medical device that causes an unexpected result is not considered a use error.

Malfunction: failure of an investigational medical device to perform in accordance with its intended purpose when used in accordance with the instructions for use or CIP, or IB.

Incident: Any malfunction or deterioration in the characteristics or performance of a device made available on the market, including use-error due to ergonomic features, as well as any inadequacy in the information supplied by the manufacturer and any undesirable side-effect.

Serious incident: Any incident that directly or indirectly led, might have led or might lead to any of the following:

- a) The death of a patient, user or other person,
- b) The temporary or permanent serious deterioration of a patient's, user's or other person's state of health,
- c) A serious public health threat

Serious public health threat: an event which could result in imminent risk of death, serious deterioration in a person's state of health, or serious illness, that may require prompt remedial action, and that may cause significant morbidity or mortality in humans, or that is unusual or unexpected for the given place and time..

Note 1: This would include events that are of significant and unexpected nature such that they become alarming as a potential serious health hazard or possibility of multiple deaths occurring at short intervals.

15.2 Causality/Relationship

The investigator and the Sponsor will assess the causality of all adverse events in relation to the research, i.e., the relationship between the AE / SAE and the investigational treatment or any other study-related procedures.

Each SAE will be classified according to four different levels of causality (as per MDCG 2020:10/1):

1) Not related: relationship to the device or procedures can be excluded when:

- the event has no temporal relationship with the use of the investigational device or the procedures;
- the serious adverse event does not follow a known response pattern to the medical device (if the response pattern is previously known) and is biologically implausible;
- the discontinuation of medical device application or the reduction of the level of activation/exposure, when clinically feasible – and reintroduction of its use (or increase of the level of activation/exposure), do not impact on the serious adverse event;
- the event involves a body-site or an organ that cannot be affected by the device or procedure;
- the serious event can be attributed to another cause (e.g. an underlying or concurrent illness/ clinical condition, an effect of another device, drug, treatment or other risk factors);
- the event does not depend on a false result given by the investigational device used for diagnosis, when applicable;

In order to establish the non-relatedness, not all the criteria listed above might be met at the same time, depending on the type of device/procedures and the serious adverse event.

2) Possible: the relationship with the use of the investigational device, or the relationship with the procedure is weak but cannot be ruled out completely. Alternative causes are also possible (e.g. an underlying or concurrent illness/ clinical condition or/and an effect of another device, drug or treatment). Cases where relatedness cannot be assessed or no information has been obtained should also be classified as possible.

3) Probable: the relationship with the use of the investigational device or the relationship with the procedure seems relevant and/or the event cannot reasonably be explained by another cause, but additional information may be obtained.

4) Causal relationship: the serious adverse event is associated with the investigational device or with procedures beyond reasonable doubt when:

- the event is a known side effect of the product category the device belongs to or of similar devices and procedures;
- the event has a temporal relationship with investigational device use/application or procedures;
- the event involves a body-site or organ that a) the investigational device or procedures are applied to or b) the investigational device or procedures have an effect on;
- the serious adverse event follows a known response pattern to the medical device (if the response pattern is previously known);
- the discontinuation of medical device application (or reduction of the level of activation/exposure) and reintroduction of its use (or increase of the level of activation/exposure), impact on the serious adverse event (when clinically feasible);
- other possible causes (e.g. an underlying or concurrent illness/ clinical condition or/and an effect of another device, drug or treatment) have been adequately ruled out;
- harm to the subject is due to error in use;

In order to establish the relatedness, not all the criteria listed above might be met at the same time, depending on the type of device/procedures and the serious adverse event.

15.3 Adverse Event Reporting

The reporting requirements adopted in this study are derived from the international standard on clinical investigations ISO 14155:2020 ("Clinical investigation of medical devices for human subjects — Good Clinical Practice"), Article 80 of the EU MDR 2017/745, and MDCG-2020-10/1:

15.3.1 Investigator reporting Responsibilities

Investigators must report to the sponsor, without delay (immediately) and not later than 3 calendar days after his awareness, all adverse device effects (ADEs), device deficiencies and serious adverse events (SAEs) study subjects experience during participation in this investigation.

Each reported event must be appropriately documented to include the event's serious criterion, relatedness, treatment, and resolution. All reported events that remain unresolved should be re-assessed until the event resolves or the subject's study participation is complete. In the event of subject death, the investigator will make reasonable effort to obtain a death summary, autopsy report, etc.

15.3.2 Sponsor's reporting Responsibilities

- 1) The sponsor will be responsible for **recording** the following events which have been documented by the investigator:
 - a) any adverse event critical to the evaluation of the results of the clinical investigation: endpoint events (mortality, ICH, and device/procedure related events) and device deficiencies that adversely affect the subject.
 - b) Any SAE (Serous Adverse Event)
 - c) Any Device Deficiency that might have led to a serious adverse vent if appropriate action had not been taken, intervention had not occurred, or circumstances had been less fortunate
 - d) Any new findings in relation to any event referred to in points (a) to (c)
- 2) The sponsor will be responsible for **reporting**, without delay to all Member States in which the clinical investigation is being conducted, the following events:
 - a) any serious adverse event that has **a causal relationship** with the investigational device, the comparator or the investigation procedure or where such causal relationship is reasonably possible
 - b) any device deficiency that might have led to a serious adverse event if appropriate action had not been taken, intervention had not occurred, or circumstances had been less fortunate
 - c) any new findings in relation to any event referred to in points (a) and (b).

The sponsor will report to all NCAs where the clinical investigation is authorised to start:

- For all reportable events as described in section 2) above resulting in death or which indicate an imminent risk of death, serious injury, or serious illness and that requires prompt remedial action for other patients/subjects, users or other persons or a new finding to it:

=> **Without delay (immediately, but not later than 2 calendar days** after awareness by sponsor of a new reportable event or of new information in relation with an already reported event.

- Any other reportable events as described in section 2) above or a new finding/update to it:
=> **Without delay (immediately), but not later than 7 calendar days** following the date of awareness by the sponsor of the new reportable event or of new information in relation with an already reported event.

It is the responsibility of sponsor to inform all investigators in writing within 10 working days if device deficiencies, adverse events, adverse device effects, near-incidents, serious adverse events, serious adverse device effects or unanticipated serious adverse device effects lead to corrective actions (e.g. change of IFU).

3) Reporting of serious incidents to the relevant CAs

- The manufacturer will report any serious incident immediately after they have established the causal relationship between that incident and their device or that such causal relationship is reasonably possible and not later than 15 days after they become aware of the incident.
- In the event of a serious public health threat a report shall be provided immediately, and not later than 2 days after the manufacturer becomes aware of that threat.
- In the event of death or an unanticipated serious deterioration in a person's state of health a report shall be provided immediately after the manufacturer has established or as soon as it suspects a causal relationship between the device and the serious incident but not later than 10 days after the date on which the manufacturer becomes aware of the serious incident.

16. SAFETY MONITORING

Synapse will designate a qualified physician to function as an independent Medical Monitor. The Medical Monitor will not otherwise be involved with the study and will act in an advisory capacity to assist the sponsor in monitoring subject safety. The Medical Monitor will review the available information (e.g., case report forms and source documentation) for site reported ADEs. The Medical Monitor will review the investigator classification of whether the event was serious, related to the study device or the procedure, and unanticipated.

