8.4 Endpoints

8.4.1 Primary Safety Endpoint

The primary safety endpoint is the incidence of serious adverse device effects (SADE), as that term is defined in Section 15.

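### The Medical Monitor's written remit covers only events the open-label site already calls device effects, so a serious event the site calls unrelated gets no independent relatedness check for the primary safety endpoint

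*Combined protocol and SAP*

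**What the plan says.** Section 8.4.1 sets the endpoint: "The primary safety endpoint is the incidence of serious adverse device effects (SADE), as that term is defined in Section 15". Section 15.1 builds that term in two steps. The first is "Adverse Device Effect (ADE): Adverse event related to the use of an investigational medical device". A SADE is then defined as "Adverse device effect that has resulted in any of the consequences characteristic of a serious adverse event". An event must therefore be judged device-related before it can be a SADE.

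Section 16 describes the only independent reader. On scope it says "The Medical Monitor will review the available information (e.g., case report forms and source documentation) for site reported ADEs". On content it says "The Medical Monitor will review the investigator classification of whether the event was serious, related to the study device or the procedure, and unanticipated". On standing it says "The Medical Monitor will not otherwise be involved with the study and will act in an advisory capacity to assist the sponsor".

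Causality is otherwise covered by 15.2: "The investigator and the Sponsor will assess the causality of all adverse events in relation to the research". Under 15.3.1 the site sends the sponsor every SAE, ADE and device deficiency within 3 calendar days of awareness, whatever the causality call. Section 7.5.1.7 has the investigator and sponsor compare adverse event incidence between arms. Section 7.1 makes the study open label at one centre, with every subject implanted. The documents describe no safety board or adjudication committee.

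**The concern.** The Monitor is asked to check relatedness, but only on events the site has already called related. A wrong 'related' call can be questioned independently; a wrong 'not related' call is not shown to the Monitor under the written remit.

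Wrong 'not related' calls are plausible here. Section 5.2 lists bleeding at electrode insertion, interference with heart rhythm and exit-site infection as theoretical device or procedure risks. Table 3 lists hemorrhage needing reoperation, cardiogenic shock or cardiac arrest, and sepsis among the complications expected in this population. Section 7.5.1.4 describes competing events as typically unrelated to device or procedure. Section 15.2 lets a 'not related' call rest partly on another cause being available, and does not require every criterion to be met. The serious events that could resemble a device effect are thus the ones most readily put down to the surgery, and that label takes them outside the Monitor's written remit.

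At stake is how far a low or zero SADE count can be trusted. Identifying safety concerns is a stated objective (6.2), and the data are to inform a multi-center pivotal trial (8.1).

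**Working it through.** The plan states no figure on this point, so there is none to reproduce. The check is a trace of the event pathway, followed by a calculation of scale.

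**Pathway, by the site's initial call**

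| Site's call | Sponsor assesses causality (15.2, 15.3.1) | Monitor reviews (16) | What the Monitor could question |
|---|---|---|---|
| Related, serious | Yes | Yes | Relatedness, seriousness, unanticipated status |
| Related, not serious | Yes | Yes | The same; an upgrade of seriousness would make it a SADE |
| Not related, serious (including death) | Yes | No written duty | Nothing |

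The third row is the gap. No section sends the Monitor unrelated SAEs, deaths, or events that the sponsor has upgraded to related.

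**Decision rule.** Section 15.2 names two assessors, Section 16 adds an advisory third, and 8.4.1 refers only to the definition. None says which judgement enters the SADE count if they differ. Section 15.2 classes unassessable cases as 'possible', but the plan does not say whether 'possible' counts as device-related for the endpoint.

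**Scale of one reclassified event.** Inputs: n = 30 implanted (8.5), and 15 per arm if allocation is exactly half (Synopsis). Limits are exact two-sided 95% (Clopper-Pearson).

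- With no events the upper limit is 1 − 0.025^(1/n). For n = 30 it is 1 − 0.025^(1/30) = 11.6%. For n = 15 it is 1 − 0.025^(1/15) = 21.8%.
- With x events the upper limit is the 0.975 quantile of Beta(x + 1, n − x).

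| Count | Rate | Exact 95% interval |
|---|---|---|
| 0/30 | 0% | 0 to 11.6% |
| 1/30 | 3.3% | 0.1 to 17.2% |
| 2/30 | 6.7% | 0.8 to 22.1% |
| 0/15 | 0% | 0 to 21.8% |
| 1/15 | 6.7% | 0.2 to 31.9% |

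These figures show what any single event does at this sample size. They do not estimate how often events would be misclassified, which the documents do not address.

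**The case against.** The other side has a good case on several points.

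- **Seriousness.** A reader might infer that independent review can only lower the SADE count. The text does not support this. The Monitor also reviews seriousness, so a non-serious ADE judged serious would become a SADE. Only the relatedness check runs one way.
- **Authority.** A reader might infer that the Monitor can strike events from the count. The role is advisory, and no section gives the Monitor's view that effect in either direction.
- **Second look.** A reader might infer that SAEs the site calls unrelated go unreviewed. They do not: the sponsor receives every one, assesses causality, and can upgrade it. That is a real safeguard, though not an independent one.
- **Other safeguards.** The comparison of adverse events between arms (7.5.1.7) and all-cause 30-day mortality (8.4.3) do not depend on attribution. The comparison is made by the same two parties, however. Because every subject is implanted, it cannot reveal harm from electrode placement that is common to both arms.
- **Size.** It is tempting to apply the Table 3 rates to the roughly 17 patients expected to have prolonged ventilation (30 × 0.565) and to say that many serious events would bypass independent review. That would count expected surgical morbidity, with overlapping categories, and not misclassified events.
- **Setting.** This is a small descriptive study of a CE-marked device, with no safety hypothesis and no numerical threshold.

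The Monitor's general role of helping to watch over subject safety might allow wider reading in practice, but nothing requires it. These arguments narrow the point and lower its weight. They do not close the gap in the relatedness check.

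**Conclusion.** The point holds in a limited form. As written, independent review of relatedness reaches only events the open-label site has already judged device-related. An SAE or death the site calls unrelated is assessed for causality by the investigator and the sponsor alone, and the plan does not say whose judgement defines a SADE when assessors disagree.

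How often this would matter cannot be derived from the documents. One reclassified event would move the endpoint from 0/30 to 1/30 and the exact upper 95% limit from 11.6% to 17.2%, assuming 30 implanted subjects as the denominator. The conclusion also takes Section 16 as the full statement of the Monitor's review duty. Severity is minor: the endpoint is descriptive, the study is a 30-patient lead-in, and the remedy is a cheap improvement.

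**What to change.** 1. Amend Section 16 so that the Medical Monitor reviews all SAEs and deaths in both arms, plus all ADEs, for seriousness and for relatedness to device or procedure.
2. State in 8.4.1 that a serious event counts as a SADE if the investigator, the sponsor or the Monitor judges it device-related, and say whether the 'possible' level in 15.2 meets that bar.
3. Report the count based on the investigator's judgement alone next to it, so that readers can see the effect of the rule.

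The any-assessor rule lets relatedness calls move the count only upward; showing both counts keeps that visible. The change needs no new staff or data collection, because the Monitor is already to be appointed and the sponsor already receives every SAE under 15.3.1. The cost is extra reading time for the Monitor and a SADE rate that may be slightly higher.
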